#### Change and Percent Change from Baseline (Day 1 prior to study IMP) in CIDBF

For 30 minutes and 45 minutes post capsaicin at each visit, change and percent change from baseline (Day 1 prior to study IMP) will be calculated. For example, change from baseline at 30 minutes post capsaicin on Day 29 is calculated as the DBF at 30 minutes post capsaicin on Day 29 minus the DBF at 30 minutes post capsaicin on Day 1 prior to study IMP. Percent change will be calculated similarly.

Summary will be presented. Between dose group comparison will be done. ANCOVA model will include dependent variable of change (or percent change) from baseline in CIDBF, with factor of dose group, and DBF at baseline (Day 1 prior to study IMP) as covariate.

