**Table 1. Objectives and Endpoints**

Objectives	Endpoints
Primary Safety and Tolerability	
To evaluate the safety and tolerability of UB-313, when administered at selected dose regimens given intramuscularly (IM) to healthy adults.	Safety will be assessed by adverse events (AEs), adverse events of special interest (AESIs), medically attended adverse events (MAAEs), local (injection site) and systemic (generalized) reactions (i.e., reactogenicity), clinical laboratory assessments (e.g., chemistry, hematology, urinalysis), vital signs, neurological and physical examinations and electrocardiograms (ECGs), through the end of study.
Primary Immunogenicity	
To evaluate the anti-Calcitonin Gene-Related Peptide (anti-CGRP) specific antibody responses to selected UB-313 dose regimens in healthy adults.	Immunogenicity will be measured serum anti-CGRP antibody titers and analyzed from baseline to Week 16 and Week 44.
Secondary	
To evaluate the effects of selected UB-313 dose regimens on capsaicin-induced dermal blood flow (DBF) as a surrogate marker of target engagement.	Pharmacodynamics (PD) of the immune response will be measured by the inhibition of capsaicin-induced increase in DBF and will be analyzed from baseline to Week 16 and until return to baseline or until Week 44, whichever comes first.
Exploratory	
To evaluate the effects of selected UB-313 dose regimens on CGRP concentrations in serum.	CGRP concentrations in serum through the end of study.
To characterize antibodies generated by UB-313.	Antibody titers against components of the UB-313 (i.e., CpG1 and UBITh1) through the end of study. Isotype-specific anti-CGRP antibody titers through the end of study.

To examine cytokine release induced by UB-313.	Cytokine release from peripheral blood mononuclear cell (PBMC)s stimulated with component of the UB-313 (T-cell ELISpot) through Week 16.
--	---

[figure not shown]

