## 5.0 Statistical Analyses

### 5.1 Immunogenicity, Pharmacodynamics, and Exploratory Analyses

Efficacy analysis will be based on FAS. All analyses and plot will be performed by dose group for each visit and each timepoint unless otherwise specified. In general, summary of a variable (e.g., titer, CIDBF) will include baseline, actual value, and change (or percent change) from baseline when applicable. Summary plots will be done when applicable.

For qualitative assessments (e.g., titer value, CIDBF...), the distribution will be examined. If the distribution is similar to log normal, log transformation will be applied. In this case, geometric mean and GMR (Geometric Mean Ratio) will be presented in place of mean and difference. For model analysis, log transformed value will be used, analysis results will be presented after anti log transformation.

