#### **5.1.2 Pharmacodynamics (PD) Analyses**

##### **5.1.2.1 Capsaicin Induced Dermal Blood Flow (Secondary Endpoint and Analysis)**

###### Capsaicin-induced increase in DBF (CIDBF)

The pharmacodynamics (PD) endpoint is the inhibition of capsaicin-induced increase in DBF (CIDBF). The DBF at each timepoint at each visit will be calculated as the average of two capsaicin-induced locations.

The DBF will be summarized for each timepoint (i.e., 0, 15, 30, 45, and 60 minutes) at each visit (i.e., Day 1, Day 29, Day 57, Day 85, Day 113, and Day 141, Day 197, Day 253, Day 309 as applicable).

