###### Change and Percent Change from pre capsaicin in CIDBF

For each post capsaicin time point at each visit, change and percent change from pre capsaicin will be calculated. For example, change at 30 minutes post capsaicin on Day 29 from pre capsaicin is calculated as the DBF at 30 minutes post capsaicin on Day 29 minus the DBF at 0-minute pre capsaicin on Day 29. Percent change will be calculated similarly.

Summary will be presented. Between dose group comparison will be done. ANCOVA model will include dependent variable of change (or percent change) from pre capsaicin in CIDBF, with factor of dose group, and DBF at 0-minute pre capsaicin as covariate.

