#### **5.1.2.3 CIDBF AUC (Exploratory)**

CIDBF AUC (0-60min) and change from baseline (Day 1 prior to study IMP) will be summarized by dose group for each visit. Between dose group comparison will be done. ANCOVA model will include dependent variable of AUC, with factor of dose group, and baseline AUC as covariate.

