#### **5.1.2.4 Inhibition Responder (Exploratory)**

CIDBF at 30 minutes post capsaicin will be used for the responder analysis. To define threshold of response, mean and standard deviation will be calculated using the assessments below.

- CIDBF at baseline from all participants

The mean minus two standard deviations (mean-2SD) will be used as the threshold of response. CIDBF responders will be defined as the participants with CIDBF less than or equal to response threshold for each visit including baseline and postbaseline visits.

Responder analysis will be done similarly to seroconversion rates.

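### The change-from-Day-1 analysis of capsaicin response uses raw blood flow, so its percent version does not measure inhibition of the capsaicin-induced increase

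*SAP*

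**What the plan says.** SAP Table 1 gives the secondary endpoint as pharmacodynamics "measured by the inhibition of capsaicin-induced increase in DBF and will be analyzed from baseline to Week 16". SAP 5.1.2.1 opens in the same terms, "The pharmacodynamics (PD) endpoint is the inhibition of capsaicin-induced increase in DBF (CIDBF", so the abbreviation belongs to the increase.

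Two modelled analyses follow in 5.1.2.1:

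- **Change from pre-capsaicin.** At each visit the 0-minute DBF is subtracted from the post-capsaicin DBF. The ANCOVA is specified "with factor of dose group, and DBF at 0-minute pre capsaicin as covariate". This is the increase, with no Day 1 response in the model.
- **Change from baseline.** For 30 and 45 minutes, the example change "is calculated as the DBF at 30 minutes post capsaicin on Day 29 minus the DBF at 30 minutes post capsaicin on Day 1", and percent change is formed the same way. The ANCOVA has dose group "and DBF at baseline (Day 1 prior to study IMP) as covariate". This has Day 1, but uses raw flow.

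Two exploratory analyses reuse the label without saying which quantity is meant. Section 5.1.2.3 states "CIDBF AUC (0-60min) and change from baseline (Day 1 prior to study IMP) will be summarized by dose group for each visit", and 5.1.2.4 states "CIDBF at 30 minutes post capsaicin will be used for the responder analysis". The general text of 5.1 adds that summaries of variables such as CIDBF include change or percent change from baseline where applicable.

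**The concern.** A percent change from Day 1 under the CIDBF label is the figure a reader would naturally quote as percent inhibition. As written, its denominator is resting flow plus the increase. Capsaicin inhibition acts on only part of that total, so the percentage is not the percentage by which the increase fell.

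The protocol synopsis (Statistical Considerations) says the Week 16 PD read-out is meant to help refine the development plan, so the size of the effect matters as well as its direction. The protocol also treats the comparison of the increase with its pre-dose level as meaningful: its rule for ending imaging after Week 16 is framed on the increase returning to baseline.

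**Working it through.** The documents state no percent-inhibition figure to reproduce, so the check is algebra on the SAP's own formulas.

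**Inputs.** R is resting (0-minute) DBF on Day 1. k is the Day 1 increase divided by R; the protocol requires at least 100% (k = 1) at Screening, and Day 1 k is not given, so k = 1 to 4 is assumed. d is the true inhibition of the increase. r is resting flow at the later visit divided by resting flow on Day 1 (assumed 0.6 to 1.2). The increase itself is taken as unaffected by r.

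Day 1 post-capsaicin DBF = R(1+k). Later post-capsaicin DBF = rR + Rk(1−d).

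**Absolute change.** Raw DBF: R[(r−1) − kd]. Increase: −Rkd. With r = 1 they are identical; for R = 100, k = 1, d = 50%, both are −50.

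**Percent change.** Raw DBF: −d·k/(1+k) + (r−1)/(1+k). Increase: −d, whatever k and r.

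With r = 1:

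| k | Share retained, k/(1+k) | Share lost, 1/(1+k) | d = 50% reads | d = 100% reads |
|---|---|---|---|---|
| 1 | 0.50 | 0.50 | −25.0% | −50.0% |
| 2 | 0.67 | 0.33 | −33.3% | −66.7% |
| 3 | 0.75 | 0.25 | −37.5% | −75.0% |
| 4 | 0.80 | 0.20 | −40.0% | −80.0% |

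With resting flow shifted, at k = 1:

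- d = 0, r = 0.8: 0 − 0.2/2 = −10%, although there is no inhibition.
- d = 30%, r = 0.6: −15% − 20% = −35%, an overstatement.
- d = 30%, r = 1.2: −15% + 10% = −5%, an understatement beyond the dilution.

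A shift common to all groups adds the same term to placebo. In this formula it cancels from the group contrast, and the dilution by k/(1+k) remains.

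**Simulation under assumed inputs.** Five arms of 8; true inhibition 40%; log-normal resting flow (log-SD 0.25) and fold increase (log-SD 0.35); Day 1-to-visit correlation 0.7. The percent contrast with placebo from the change-from-baseline model averages about −21, −27 to −28 and −31 points at k = 1, 2 and 3, close to 40 × k/(1+k) = 20, 26.7 and 30. Dividing the adjusted difference by the adjusted placebo mean gives a median of 39.9% for the percent pre-capsaicin analysis and 39.8% for a model of the percent increase adjusted for its Day 1 value. Both recover the truth.

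**Precision of the Day 1-adjusted increase against the pre-capsaicin analysis, k = 2** (SE, pre-capsaicin v Day 1-adjusted):

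- Percent scale, no reading noise: 0.320 v 0.308 at correlation 0.3, and 0.320 v 0.240 at 0.7.
- Percent scale, correlation 0.7, reading noise log-SD 0.20: 0.515 v 0.522.
- Absolute scale, correlation 0.3, no reading noise: 0.346 v 0.396, which is 14% higher.

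**Responder threshold.** Mean − 2SD equals mean × (1 − 2CV), so it is negative once the CV exceeds 50%. For a log-normal fold increase at k = 2 it is 0.59 with log-SD 0.35 and −0.15 with log-SD 0.50.

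**The case against.** The strongest answer is that the endpoint is already estimated properly. The pre-capsaicin analysis compares the increase with concurrent randomised placebo at every visit, without dilution. With a placebo arm, a Day 1 term is a matter of precision, not validity, and the simulations show that the gain can vanish or reverse. This stands, and it limits the harm.

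Second, the general text of 5.1 names CIDBF among the variables to be summarised with change from baseline, so a descriptive change in the increase may be produced anyway. This stands in part. The rule is generic and conditional, specifies no model, and does not override the explicit raw-DBF formula in 5.1.2.1.

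Third, the worked example says openly that DBF is what is subtracted, the SAP does not say that this percentage will be reported as inhibition, and the documents tie no decision threshold or power target to it. This is fair: the harm depends on how the figure is used. But the subsection heading calls it change in CIDBF, and that invites the use.

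Fourth, k = 1 is the eligibility floor, so the 50% loss is the extreme for a participant who just qualified at Screening. This is also fair, although the criterion applies at Screening only and does not bound k on Day 1.

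**Conclusion.** The concern holds on the percent scale. The stated formula does not measure the stated endpoint: with stable resting flow it shows k/(1+k) of the true inhibition, a relative understatement of 1/(1+k), or 50%, 33% and 25% at k = 1, 2 and 3. No model specified in 5.1.2.1 takes the increase relative to its Day 1 value.

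A reader might infer three stronger things that the documents do not support:

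- That the plan always understates inhibition. The direction is fixed only when resting flow is stable; otherwise the percent version can overstate inhibition or show it where there is none.
- That the absolute change is biased too. With stable resting flow it equals the change in the increase exactly; it is affected only if resting flow shifts.
- That the secondary endpoint lacks a valid analysis. The pre-capsaicin comparison provides one.

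The factor is exact under equal resting flow. Day 1 k, resting-flow variability, correlations and reading noise are not in the documents, so every figure that depends on them is an assumption.

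**What to change.** In the change-from-baseline subsection of SAP 5.1.2.1:

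- Define change and percent change from Day 1 on the increase: DBF at 30 or 45 minutes minus the same-visit 0-minute DBF.
- Use the Day 1 increase at the same time point as the ANCOVA covariate.
- Report percent inhibition against placebo as the adjusted difference divided by the adjusted placebo mean of that visit's increase. If the rule in 5.1 applies ("If the distribution is similar to log normal, log transformation will be applied"), report a ratio of geometric means of the increase, with a stated rule for non-positive increases.
- Keep the pre-capsaicin analysis. Label any raw-DBF change as total flow, not inhibition.

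In 5.1.2.3 and 5.1.2.4, state whether CIDBF is raw DBF or the increase. If the increase is used for responders, check that the mean − 2SD threshold is attainable. Below zero, only a participant whose flow fell after capsaicin could count as a responder.

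The cost is SAP wording and reprogramming of derived variables. The 0-, 30- and 45-minute readings are already planned at each challenge visit. The 0-minute reading adds some noise, and no precision gain over the pre-capsaicin analysis is guaranteed. The case for the change is that the reported percentage would then match the endpoint.

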#### DBF for Non-capsaicin Vehicle Control

DBF from control location (vehicle RD) will be summarized for each dose group and each visit as well as for pooled group and all visits.

#### **5.1.2.2 CIDBF by Gender (Exploratory)**

DBF and change from pre capsaicin will be summarized by gender for baseline, week 16 and week 44.

#### **5.1.2.3 CIDBF AUC (Exploratory)**

CIDBF AUC (0-60min) and change from baseline (Day 1 prior to study IMP) will be summarized by dose group for each visit. Between dose group comparison will be done. ANCOVA model will include dependent variable of AUC, with factor of dose group, and baseline AUC as covariate.

#### **5.1.2.4 Inhibition Responder (Exploratory)**

CIDBF at 30 minutes post capsaicin will be used for the responder analysis. To define threshold of response, mean and standard deviation will be calculated using the assessments below.

- CIDBF at baseline from all participants

The mean minus two standard deviations (mean-2SD) will be used as the threshold of response. CIDBF responders will be defined as the participants with CIDBF less than or equal to response threshold for each visit including baseline and postbaseline visits.

Responder analysis will be done similarly to seroconversion rates.

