	
Cohort 3 may begin dosing at least 24 hours after all participants in Cohort 2 have received their first dose, and available (blinded) safety and tolerability data have been reviewed by the SRC. Based on the available data, a decision will be made to begin dosing of Cohort 3.
 
Participants will be provided with a diary. Starting the day of IMP administration, they will fill in the diary daily for 7 days, recording their temperature, and any solicited local and systemic symptoms of reactogenicity.
 
Capsaicin Challenge
 
A capsaicin-induced increase in DBF model will be used to assess the PDs of the UB-313-mediated immune response. Personnel who will perform these assessments will not be involved in UB-313 safety and tolerability evaluation due to the potential of unblinding. The capsaicin challenge will be conducted at Screening, Baseline before the first dose, and every 4 weeks up to Week 20 and subsequently every 8 weeks until the end of study at Week 44. After Week 16, LSCI assessment may no longer be required once the average capsaicin induced DBF increase within that cohort has returned to baseline (i.e., DBF response ± 2 SD before administration of IMP within a cohort).

Total Expected Number of Participants	Approximately 40 eligible healthy male and female participants (10 per cohort) will be enrolled to receive UB-313 or placebo.
Main Inclusion Criteria	
Full details of inclusion criteria are listed in the protocol. The main inclusion criteria include:
 
• Is a male or female aged 18 to 55 years old, inclusive, at time of informed consent.• Has a body mass index between 18 and 30 kg/m², inclusive at Screening, and with a minimum weight of 50 kg.• Male participants and their partners of childbearing potential must commit to the use of highly effective contraceptives for the study duration and for at least 12 weeks after the last dose. Men must refrain from donating sperm during this same period.• Female participants must be of nonchildbearing potential, or, for women of childbearing potential, must be willing to practice highly effective contraception throughout the duration of the study and for at least 24 weeks following the last dose.

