#### **5.1.2.5 Duration of Inhibition Response (Exploratory)**

Duration of inhibition response is defined as from baseline to either return to baseline or until Week 44, whichever comes first for inhibition responders. Participants who do not return to baseline will be censored at the time of study exit.

Duration of inhibition response will be summarized for each dose group, using Kaplan-Meier product-limit estimates.

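### The inhibition-responder cut-off ignores each participant's own baseline, so responder status in SAP 5.1.2.4, and entry to the duration analysis, depends strongly on baseline flow

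*SAP*

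**What the plan says.** SAP 5.1.2.4 fixes the time point ("CIDBF at 30 minutes post capsaicin will be used for the responder analysis") and takes the mean and SD from "CIDBF at baseline from all participants". The cut-off follows: "The mean minus two standard deviations (mean-2SD) will be used as the threshold of response". Each visit, baseline included, is then compared with it: "CIDBF responders will be defined as the participants with CIDBF less than or equal to response threshold for each visit". Responder rates are handled like the seroconversion rates in SAP 5.1.1.3, with a comparison against placebo.

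SAP 5.1.2.5 estimates duration of inhibition by Kaplan-Meier, up to return to baseline or Week 44, "whichever comes first for inhibition responders".

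Three other places bear on the point:

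- SAP 5.1 names CIDBF among the variables to be log-transformed if they look log-normal. It does not say whether this reaches the responder threshold.
- SAP 5.1.2.1 introduces CIDBF as the capsaicin-induced increase in flow. Its worked example for change from baseline in CIDBF uses the raw flow at 30 minutes.
- The Protocol Synopsis provides two pre-dose challenges: "The capsaicin challenge will be conducted at Screening, Baseline before the first dose". Entry requires at least a 100% increase in flow at Screening.

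**The concern.** Inhibition is a change within a person. This rule instead asks whether a person's flow is low compared with everyone's flow at baseline. Someone with naturally low flow can cross the line with little inhibition, while someone with high flow can be strongly inhibited and miss it. Because the rule is also applied at baseline, a participant can be an inhibition responder before any dose.

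Each active group has 8 participants, so chance differences in baseline flow between groups can look like differences between regimens. The duration analysis inherits the selection, and the Protocol Synopsis makes duration of response the purpose of the phase after Week 16.

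**Working it through.** The documents give no mean, SD or CV for CIDBF and no target inhibition, so there is no plan figure to reproduce.

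**From the documents:** the cut-off rule, the 30-minute time point, about 40 participants, 8 pooled placebo participants, and the log option.

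**Assumed:** a true inhibition of 50%; within-person CV w = 15% (20% as an alternative); between-person CV b from 10% to 40%; independent visit-to-visit variation; and a cut-off treated as known.

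**1. Inhibition needed to qualify (natural scale).** Set the baseline mean to 1 and the total baseline CV to T. The cut-off is 1 − 2T, and a person with baseline x needs inhibition of 1 − (1 − 2T)/x. At T = 0.30 the cut-off is 0.40:

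- 1 SD below the mean: 1 − 0.40/0.70 = 43%
- at the mean: 1 − 0.40/1.00 = 60%
- 1 SD above the mean: 1 − 0.40/1.30 = 69%

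The cut-off reaches zero at T = 0.50.

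**2. Sensitivity on the natural scale.** With T ≈ √(b² + w²), P ≈ Φ((0.5 − 2T)/(0.5T)). At b = 20% and w = 15%, T = 0.25, the cut-off is 0.50 and P = Φ(0) = 50%. Simulation with normal person levels multiplied by normal visit errors gives 51%. The table shows the simulated values.

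**3. Sensitivity on the log scale.** With s_b² = ln(1 + b²) and s_w² = ln(1 + w²), P = Φ(ln 2/√(s_b² + s_w²) − 2). At b = 20% and w = 15%, the root is 0.248 and P = Φ(2.796 − 2) = 79%.

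**4. Own-baseline rule.** A participant responds if ln(visit/Day 1) ≤ −2√2·s_w. Then P = Φ(ln 2/(√2·s_w) − 2). At w = 15%, s_w = 0.149 and P = Φ(3.286 − 2) = 90%, whatever b is. The false-responder rate is Φ(−2) = 2.3%.

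| Between-person CV (w = 15%) | SAP rule, natural | SAP rule, log | Own baseline |
|---|---|---|---|
| 10% | 93% | 97% | 90% |
| 15% | 76% | 90% | 90% |
| 20% | 51% | 79% | 90% |
| 30% | 14% | 54% | 90% |
| 40% | 4% | 37% | 90% |

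**5. When the own-baseline rule is more sensitive.** The formulas in steps 3 and 4 differ only in the divisor, √(s_b² + s_w²) against √2·s_w. The own-baseline rule therefore beats the log-scale SAP rule only when s_b exceeds s_w. At w = 20% it flags 68%. The log-scale SAP rule flags 79% at b = 15% and 68% at b = 20%.

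**6. Dependence on flow level.** At b = 20% and w = 15%, split participants into thirds by underlying flow and give all of them the same true 50% inhibition. The SAP rule flags 91% of the lowest third and 14% of the highest on the natural scale, and 99% against 47% on the log scale. The own-baseline rule flags about 90% in each third.

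**7. If CIDBF means raw flow.** Halving an f-fold increase multiplies flow by r = (1 + 0.5f)/(1 + f). The SAP rule then flags half of participants at a total CV of (1 − r)/2: 12.5% for a 100% increase (r = 0.75) and 20.8% for a 500% increase (r = 0.583). On the increase itself the matching CV is 25% (natural scale) or about 36% (log scale).

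**The case against.** The rule is a reference limit, and the SAP uses the same form for antibody response (mean plus 2 SD, SAP 5.1.1.3). Responder status is reported at baseline and compared with placebo, so chance low-flow responders are visible. The analysis is labelled exploratory in an unpowered first-in-human study. SAP 5.1.2.1 already gives change and percent change from own baseline at 30 and 45 minutes, with a baseline-adjusted ANCOVA. All of this stands and limits the impact. It does not make the rule a measure of inhibition: a placebo comparison shows the false-responder rate but does not recover inhibited high-flow participants.

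A reader might infer that a participant with a true 50% inhibition is usually classed as a non-responder. The documents do not support that. They give no CV, the 50% is an assumption, and at a between-person CV of 10% the rule flags 93%. A reader might also infer that nobody could respond. That would need the natural scale, a total baseline CV of about 50% or more, and a measure that stays positive. On the log scale the cut-off is always above zero.

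An own-baseline rule has limits too. It is not always more sensitive (step 5). A chance-low Day 1 reading also makes it harder to meet, so some dependence on the observed Day 1 value remains even though dependence on underlying flow is removed.

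**Conclusion.** The structural point needs no assumption: the responder definition does not use the participant's own Day 1 value, and SAP 5.1.2.5 carries that selection into the duration analysis. How much sensitivity is lost cannot be fixed from the documents. Under the stated assumptions it runs from nearly all participants flagged to almost none, depending on the baseline CV, the scale and the meaning of CIDBF, none of which SAP 5.1.2.4 settles. The case for change rests on the dependence on flow level (91% against 14%, or 99% against 47% on the log scale, in the example) rather than on a uniform gain in sensitivity. The change should be made, but the impact is moderate, because the analysis is exploratory and within-person change is already analysed as a continuous measure.

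**What to change.** 1. In SAP 5.1.2.4, state whether CIDBF is the increase or the raw flow at 30 minutes, and on which scale the threshold is set.
2. Define a responder by the participant's own log ratio (or percent change) from Day 1 at 30 minutes falling below minus 2 SDs of that change.
3. Estimate that SD mainly from pooled placebo changes. Use Screening-to-Day 1 pairs only as support: Screening values are truncated by the 100% entry criterion, so those differences are open to regression to the mean.
4. Use the same definition to select participants for SAP 5.1.2.5.
5. Keep the mean-minus-2-SD rule as a sensitivity analysis.

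The cost is SAP wording and a little programming, with no new data. The real drawback is that the SD of change comes from few participants. With 8 placebo participants at one visit (7 degrees of freedom), its 95% interval runs from √(7/16.01) = 0.66 to √(7/1.69) = 2.04 times the estimate. Pooling placebo visits helps, though they share one Day 1 value and are not independent.
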